7.3 Recording/Reporting requirements

7.3.1 Eliciting AE Information

Research subjects will be routinely questioned about AEs at study visits.

7.3.2 Recording Requirements

All observed or volunteered adverse events (serious or non-serious) and abnormal test findings, regardless of study group or suspected causal relationship to the study drug(s) will be recorded in the subjects' case histories. For all adverse events, sufficient information will be pursued and/or obtained so as to permit 1) an adequate determination of the outcome of the event (i.e., whether the event should be classified as a *serious adverse event*) and; 2) an assessment of the causal relationship between the adverse event and the study drug(s).

AEs or abnormal test findings felt to be associated with the investigational drug or study treatment(s) will be followed until the event (or its sequelae) or the abnormal test finding resolves or stabilizes at a level acceptable to the investigator (i.e., study site principal investigator) or sponsor.

7.3.3 Abnormal Test Findings

An abnormal test finding will be classified as an *adverse event* if one or more of the following criteria are met:

- The test finding is accompanied by clinical symptoms.
- The test finding necessitates additional diagnostic evaluation(s) or medical/surgical intervention; including significant additional concomitant drug treatment or other therapy.

Note: simply repeating a test finding, in the absence of any of the other listed criteria, does not constitute an AE.

- The test finding leads to a change in study drug dosing or discontinuation of subject participation in the clinical study.
- The test finding is considered an AE by the investigator (i.e., study site principal investigator) or sponsor of the IND application.

7.3.4 Causality and severity assessment

The investigator (i.e., study site principal investigator) or sponsor of the IND application will promptly review documented adverse events and abnormal test findings to determine 1) if the abnormal test finding should be classified as an adverse event; 2) if there is a reasonable

possibility that the adverse event was caused by the study drug(s); and 3) if the adverse event meets the criteria for a *serious adverse event*.

If the investigator (i.e., study site principal investigator) or sponsor's final determination of causality is "unknown and of questionable relationship to the study drug(s)", the adverse event will be classified as *associated with the use of the study drug(s)* for reporting purposes. If the investigator (i.e., study site principal investigator) or sponsor's final determination of causality is "unknown but not related to the study drug(s)", this determination and the rationale for the determination will be documented in the respective subject's case history.

7.4 Reporting of Suspected Adverse Reactions

All events meeting the definition of a serious adverse event should be recorded on a MedWatch 3500A Form

(<http://www.fda.gov/downloads/AboutFDA/ReportsManualsForms/Forms/UCM048334.pdf>) or departmental SAE form. Copies should be sent to the Sponsor, Investigator, [contact], and the local Institutional Review Board per institutional reporting requirements.

In addition to completing appropriate patient demographic and suspect medication information, the report should include as applicable the following information that is available at the time of report within the Event Description (section 5) of the MedWatch 3500A form:

- CTCAE term(s) and grade(s)
- current status of study drug
- all interventions to address the AE (testing and result, treatment and response)
- hospitalization and/or discharge dates
- event relationship to study drug

Follow-up reports:

Additional information may be added to a previously submitted report by adding to the original MedWatch 3500A report and submitting it as follow-up or creating supplemental summary information and submitting it as follow-up with the original MedWatch 3500A form.

7.5 Review of Safety Information: Sponsor Responsibilities¹

The sponsor must promptly review all information relevant to the safety of the drug obtained or otherwise received by the sponsor from foreign or domestic sources, including information derived from any clinical or epidemiological investigations, animal or in vitro studies, reports in the scientific literature, and unpublished scientific papers, as well as reports from foreign regulatory authorities and reports of foreign commercial marketing experience for drugs that are not marketed in the United States.

¹ [21 CFR Sec. 312.50](http://www.fda.gov/8000/CFR/Title21/Part312/Section312.50.html)

7.6 Review of Safety Information: Investigator Responsibilities²

An investigator shall promptly report to the sponsor of the IND application any adverse effect that may reasonably be regarded as caused by, or probably caused by, the drug. If the adverse effect is alarming, the investigator shall report the adverse effect immediately. An investigator shall provide the sponsor with an adequate report shortly after completion of the investigator's participation in the investigation.

7.7 Reporting of Adverse Reactions to the FDA

Reporting of serious adverse events to the FDA will follow 21 CFR 312.32.

7.7.1 Written IND safety reports

The Sponsor will submit a written IND Safety Report (i.e., completed FDA Form 3500 A) to the responsible new drug review division of the FDA for any observed or volunteered adverse event that is determined to be a *serious and unexpected, suspected adverse reaction*. Each IND Safety Report will be prominently labeled, “IND Safety Report”, and a copy will be provided to all participating investigators (if applicable) and sub-investigators.

Written IND Safety Reports will be submitted to the FDA as soon as possible and, in no event, later than 15 calendar days following the Sponsor receipt of the respective adverse event information and determination that it meets the respective criteria for reporting.

For each written IND Safety Report, the Sponsor will identify all previously submitted IND Safety Reports that addressed a similar suspected adverse reaction experience and will provide an analysis of the significance of newly reported, suspected adverse reaction in light of the previous, similar report(s) or any other relevant information.

Relevant follow-up information to an IND Safety Report will be submitted to the applicable review division of the FDA as soon as the information is available and will be identified as such (i.e., “Follow-up IND Safety Report”).

If the results of the Sponsor’s follow-up investigation show that an adverse event that was initially determined to not require a written IND Safety Report does, in fact, meet the requirements for reporting; the Sponsor will submit a written IND Safety Report as soon as possible, but in no event later than 15 calendar days, after the determination was made.

7.7.2 Telephoned IND safety reports – fatal or life-threatening suspected adverse reactions

In addition to the subsequent submission of a written IND Safety Report (i.e., completed FDA Form 3500A), the Sponsor will notify the responsible review division of the FDA by telephone or facsimile transmission of any *unexpected, fatal or life-threatening suspected adverse reaction*.

The telephone or facsimile transmission of applicable IND Safety Reports will be made as soon

² [21 CFR Sec. 312.64](#)

as possible but in no event later than 7 calendar days after the Sponsor's receipt of the respective adverse event information and determination that it meets the respective criteria for reporting.

7.8 Reporting Adverse Events to the Responsible IRB

In accordance with applicable policies of the University of Pittsburgh Institutional Review Board (IRB), the Investigator will report, to the IRB, any observed or volunteered adverse event that is determined to be 1) *associated with the investigational drug or study treatment(s)*; 2) *serious*; and 3) *unexpected*. Adverse event reports will be submitted to the IRB in accordance with the respective IRB procedures.

Applicable adverse events will be reported to the IRB as soon as possible and, in no event, later than 10 calendar days following the investigator's receipt of the respective information. Adverse events which are 1) *associated with the investigational drug or study treatment(s)*; 2) *fatal or life-threatening*; and 3) *unexpected* will be reported to the IRB within 24 hours of the Investigator's receipt of the respective information.

Follow-up information to a reported adverse event will be submitted to the IRB as soon as the relevant information is available. If the results of the Investigator's follow-up investigation show that an adverse event that was initially determined to not require reporting to the IRB does, in fact, meet the requirements for reporting; the Investigator will report the adverse event to the IRB as soon as possible, but in no event later than 10 calendar days, after the determination was made.

8. PHARMACEUTICAL INFORMATION

A list of the adverse events and potential risks associated with the investigational and commercial agents administered in this study can be found in Section 7.1.

This Phase 1/2 trial will evaluate the effectiveness of autologous α DC1 (alpha dendritic cell type 1 loaded with autologous tumor material) vaccines, combined with a systemic chemokine modulation regimen [CKM; intravenous rintatolimod (TLR3 ligand, a derivative of Poly-I:C) + intravenous IFN α + oral celecoxib] as adjuvant therapy, after cytoreductive surgery (CRS) and locoregional hyperthermic intraperitoneal chemotherapy (HIPEC) in patients with potentially resectable peritoneal surface malignancies (PSM), including but not limited to malignant peritoneal mesothelioma and peritoneal carcinomatosis (PC) of appendiceal and colorectal origin. The primary outcome measure will be recurrence free survival.

8.1 DC Vaccine

Dendritic cells (DC) are derived from autologous (the patient's own) adherent mononuclear cells (monocytes) in the peripheral blood by 5-day or 6- day culture in the presence of interleukin 4 (IL-4) and granulocyte-macrophage colony stimulating factor (GM-CSF), followed by 1-2 days of maturation. The autologous tumor tissue needed for manufacturing of the vaccine is acquired from surgery that is performed as part of the patient's standard of care for their cancer as determined by their treating physician.

8.1.1 Other names

Alpha-type-1 polarized dendritic cells, alpha DC1, α DC1

8.1.2 Formulation

The DC Vaccine will be prepared in the cGMP facility of the University of Pittsburgh Cancer Institute, in a process analogous to the existing BB-IND 13,234 (colorectal cancer). The α DC1 vaccines are prepared in the University of Pittsburgh Immunotransplantation Center (ITC) under cGMP conditions and the final product is vialled and cryopreserved. Labels placed on all tubes contain a unique vaccine lot. The vaccine release will follow the quality and safety testing performed by the ITC. The target dose of α DC1 vaccine is 3×10^6 cells in 0.5 mL for each injection, intranodal and intradermal, however, in case of manufacturing limitations; a minimum of 0.5×10^6 cells is acceptable per injection site (0.5×10^6 cells total). Patients can receive a lesser number of vaccine DCs, but any such patients will not be included in the analysis of the primary endpoint.

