The Phase 2 immunotherapy regimen will include 1 priming dose of the α DC1 vaccine and 3 booster doses of the α DC1 vaccine combined with CKM. Each dose of vaccine, whether priming or booster, will include 1 intranodal (3M cells) and 1 intradermal (3M cells) injection. Phase 1 includes only the priming vaccine dose and 1 cycle of a booster dose + CKM.

Each booster vaccine dose (booster cycles 1-3) will be followed by 4-days of systemic CKM which is comprised of intravenous (IV) IFN α (dose-escalation in Phase 1 only: 5-20 MU/m 2) once a day for 4 days; IV rintatolimod (short-half-life TLR3 ligand) 200 mg on Wednesday and Friday only of the CKM regimen; and oral celecoxib 200 mg twice a day for all 5 days.

In order to avoid overlap between experimental immunotherapy and potential adjuvant chemotherapy (which can be clinically indicated as a part of standard care in a subset of patients), the experimental treatment may be interrupted after each cycle to allow adjuvant chemotherapy that may be done for each patient's clinical care, not as part of this research study. If clinically indicated any cycle of adjuvant chemotherapy may start a minimum of 5 days after completion of a cycle of immunotherapy and recovery from any potential side effects. The following cycle of immunotherapy may start at least 5 days after the completion of chemotherapy and after recovery from acute side effects of chemotherapy.

Timing of the experimental treatment:

- Priming cycle (vaccine alone): 6 to 16 weeks after surgery (target: 8 weeks)
- Booster cycle 1 (vaccine plus CKM): 4 to 12 weeks after priming cycle (target: 4 weeks)
- Booster cycle 2 (vaccine plus CKM): 4 to 12 weeks after booster cycle 1 (target: 4 weeks)
- Booster cycle 3 (vaccine plus CKM): 4 to 12 weeks after booster cycle 2 (target: 4 weeks)

The primary endpoint will be time to tumor progression/recurrence on CT or MR imaging. Secondary endpoints will be immunologic response markers.

UPCI #: 12-110

Version Date: 03-18-2016

The schemas for the trial are located in Sections 5.1 and 5.2.

TABLE OF CONTENTS

SCHEMA.....	2
LIST OF ABBREVIATIONS.....	6
1. OBJECTIVES	8
1.1 Primary Objectives.....	8
1.2 Secondary Objectives.....	8
2. BACKGROUND	8
2.1 Tumor Immunogenicity in Malignant Peritoneal Mesothelioma.....	8
2.2 Tumor Immunogenicity in Colorectal Adenocarcinoma with Peritoneal Carcinomatosis.....	10
2.3 Tumor Immunogenicity in Appendiceal Adenocarcinoma with Peritoneal Carcinomatosis.....	11

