5.1 Phase 1: Dose assessment of α DC1 vaccine chemokine-modulatory regimen (CKM)

The recommended Phase 2 dose of the combination of α DC1 vaccine in combination with IFN α , rintatolimod, and celecoxib will be established by administering fixed doses of the vaccine, rintatolimod, and celecoxib in combination with escalating doses of IFN α . Patients will receive a priming dose of the vaccine which consists of 1 intranodal injection followed by 1 intradermal injection on the Monday of the first week. Patients will then receive a booster dose of the DC vaccine, which consists of 1 intranodal injection and 1 intradermal injection, on Monday followed by the CKM regimen on days Tuesday through Friday of the booster cycle.

There will be 3 dose finding cohorts with one additional de-escalation cohort (designated -1) if needed, as shown in the table below:

Phase 1 Dose Tiers	α DC1 Vaccine (IN + ID)***	Components of CKM cycle		
		IFN α (MU/M ² IV) Days T-F	Rintatolimod* (mg, IV) Days W&F	Celecoxib** (mg, orally, twice a day) Days T-F
-1	3+3 M cells	5	100	200
1	3+3 M cells	5	200	200
2	3+3 M cells	10	200	200
3	3+3 M cells	20	200	200

*Rintatolimod starting dose will be 200 mg unless dose escalation is from tier -1 in which case cohorts 2 and 3 will use 100 mg of rintatolimod.

**Celecoxib will be administered orally, at a dose of 200 mg, once a day starting the day of the first vaccine (day 1 of week 1) and continue until Friday the last day of the CKM regimen. The dose will be increased to 200 mg, twice a day on the days of vaccination (Monday) and over the 4 days of chemokine modulation regimen (Tuesday - Friday).

***In case of limited availability of vaccine, the treatment may proceed with reduced numbers of the cells (down to 0.5 M IN + 0.5 M ID for each vaccination cycle).

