5.4.2 DC vaccine administration

The intranodal and intradermal administration of the DC vaccine will be performed by the investigator/sub-investigator or their designee.

5.4.2.1 *Intra-nodal administration*

The priming dose of vaccine may be administered on any day of the week since it is not followed by the CKM regime. The intranodal injection for the booster doses will be administered on Monday of cycles 1 through 3.

Intranodal administration will consist of ultrasound-guided intranodal injections of the autologous tumor α DC1 vaccine at a target dose of 3×10^6 in 0.5 mL. Due to manufacturing limitations a minimum of 0.5×10^6 cells is acceptable. In order to avoid repetitive scarification of a single lymph node, the patients will have subsequent doses administered at 3 different sites, with the sites rotated as follows: (a) right inguinal lymph nodal group, (b) left inguinal lymph nodal group, (c) right axillary lymph nodal group, and (d) left axillary lymph nodal group. Only one lymph node will be injected at each visit with the dendritic cells. The size of the lymph node to be injected will be a minimum of 5 mm and a maximum size of 20 mm.

5.4.2.2 *Intradermal route*

Intradermal injection will be used to complement the intranodal injections (provide a depot effect) and it can be used as the only route (for all DCs) in case intranodal injection is not feasible. Each portion of the vaccine will be administered using a 1 mL syringe and needle appropriate for intradermal injections and will hold 0.5 mL of the vaccine preparation. The intradermal DC vaccine should be injected in the vicinity of the major nodal basin of the thigh. The nodal basin must not have been previously dissected.

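### Section 8.1.2 gives the minimum vaccine dose as both 0.5 million cells per injection site and 0.5 million in total, so membership of the primary analysis is undefined for some reduced-dose patients

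*Combined protocol and SAP*

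**What the plan says.** The Schema states that each dose, priming or booster, "will include 1 intranodal (3M cells) and 1 intradermal (3M cells) injection". The target is therefore 6 million cells per vaccination.

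Section 8.1.2 allows a lower dose when manufacturing is limited. It says that 0.5 million "cells is acceptable per injection site", and a parenthesis in the same sentence gives 0.5 million as the total. The next sentence removes patients given fewer cells from the primary-endpoint analysis: "Patients can receive a lesser number of vaccine DCs, but any such patients will not be included in the analysis of the primary endpoint".

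Three other places bear on the minimum:

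- The footnote to the dose-tier table in Section 5.1 lets treatment proceed with reduced numbers, "down to 0.5 M IN + 0.5 M ID for each vaccination cycle".
- Section 5.4.2.1 gives a minimum of 0.5 million for the intranodal injection.
- Section 5.4.2.2 says of the intradermal route that "it can be used as the only route (for all DCs) in case intranodal injection is not feasible", and states no separate minimum for that case.

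Section 13.3 analyses evaluable patients and gives no dose threshold.

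**The concern.** The minimum dose is more than a manufacturing tolerance, because Section 8.1.2 makes it the criterion for entering the primary analysis. If the sentence supports two thresholds, the analysis set is not fixed in advance for patients who fall between them.

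The trial is open and single-arm, and it tests progression against historical medians of 20, 20 and 12 months taken from the literature (Section 13.2). Whoever settles the threshold could do so with the progression times in view. Nothing in the plan applies a matching cell-dose filter to the historical figures. A rule that drops treated patients by the dose they received therefore acts on one side of the comparison only.

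**Working it through.** **Inputs.** Two injections per dose, 3 million cells each (Schema). Minimum of 0.5 million per site, and 0.5 million in total (both Section 8.1.2). Minimum of 0.5 million intranodal plus 0.5 million intradermal (Section 5.1 footnote). Minimum of 0.5 million intranodal (Section 5.4.2.1).

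**Step 1: reproduce the stated total.** Total = number of sites × per-site minimum.

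- Two sites: 2 × 0.5 = 1.0 million. The stated 0.5 million is not reproduced.
- One site: 1 × 0.5 = 0.5 million. The stated total is reproduced only here.

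The two figures in Section 8.1.2 therefore differ by 1.0 / 0.5 = 2-fold for the standard dose.

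**Step 2: compare with the other sections.** The Section 5.1 footnote gives 0.5 + 0.5 = 1.0 million. Section 5.4.2.1 gives 0.5 million for one of the two injections. Both agree with the per-site figure. There are two conflicting thresholds for a two-site dose: 0.5 in each site, or 0.5 overall.

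**Step 3: classify patients under each wording of Section 8.1.2** (million cells).

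| Intranodal | Intradermal | Total | At least 0.5 at each site used | At least 0.5 in total |
|---|---|---|---|---|
| 0.2 | 0.2 | 0.4 | out | out |
| 0.25 | 0.25 | 0.5 | out | in |
| 0.4 | 0.4 | 0.8 | out | in |
| 0.49 | 0.5 | 0.99 | out | in |
| 0.5 | 0.5 | 1.0 | in | in |
| 0.3 | 0.9 | 1.2 | out | in |
| 0.4 | 3.0 | 3.4 | out | in |
| none | 0.5 | 0.5 | in | in |
| none | 0.8 | 0.8 | in | in |

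The pattern is general. If two sites share a total below 1.0 million, at least one holds less than 0.5 million, so the per-site wording excludes the patient; the total wording includes the patient once the total reaches 0.5 million. At 1.0 million or more, the wordings still disagree whenever one site is below 0.5 million. For a patient treated by the intradermal route alone they agree.

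**Step 4: look for a rule elsewhere.** Section 13 gives no threshold. Section 8.1.2 also does not say whether one low dose among the four vaccinations is enough to exclude a patient.

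**The case against.** The strongest reply is that the parenthetical total is a slip. The per-site figure, the Section 5.1 footnote and Section 5.4.2.1 amount to one rule, and only the parenthesis departs from it. A reader might count three competing minimums; the documents support two. That the per-site figure appears more often does not make it the right one, and as written the sentence still gives two answers.

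It is also fair to say that the Section 5.1 footnote concerns whether Phase 1 treatment may proceed and does not define an analysis set. The conflict that matters lies inside Section 8.1.2. Nor is every reduced-dose patient unclassifiable: under Section 8.1.2, intradermal-only patients are classified the same way by both figures.

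A reader might infer a loss of power. The documents do not support a figure. They give no share of patients below either threshold, and Section 3 says that a patient excluded for any reason during the study will be replaced. Whether that covers exclusion from the analysis set is unclear, but if it does the number analysed need not fall.

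A reader might also infer that dropping low-dose patients favours the vaccine. No section links cell number to progression; Section 2.5 names IL-12 production by the cells as the best predictor in the earlier glioma study. The product is also vialled, frozen and release-tested before use, so its cell number is largely known before vaccination and does not depend on later progression. The direction of any bias is therefore not shown. What remains is that the threshold is not fixed, and that the filter has no counterpart in the historical medians.

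Finally, an evaluable-patient analysis is a prespecified choice. That is true, but evaluable is not defined by a single dose rule.

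**Conclusion.** The point holds as an internal contradiction with a direct effect on the primary analysis set. The two figures in Section 8.1.2 differ two-fold for the standard two-injection dose. The patients affected are those treated at two sites with a total from 0.5 to below 1.0 million, or with one site below 0.5 million whatever the total. How many there will be is not given, and neither the direction nor the size of any effect on the estimate can be derived from the documents. The sample size of 168 in Section 13.2 is not called into question by this point.

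The conclusion assumes that a lesser number means fewer cells than the stated minimum. The phrase could also be read as fewer than the 3 million target per injection, which would exclude every reduced-dose patient. The amendment should close off that reading too.

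**What to change.** 1. In Section 8.1.2, reconcile the per-site and total figures with each other and with Sections 5.1 and 5.4.2, so that one threshold applies. The value is for the sponsor. State whether the threshold applies to each vaccination, and how it applies when only the intradermal route is used.
2. In Section 13.3, make the primary time-to-progression analysis one of all vaccinated patients with no dose-based exclusion. Report the subset that met the minimum dose as a sensitivity analysis.
3. Align this with the other primary-analysis exclusions: cycles outside their windows and late priming (Section 5.2), and patients removed from treatment (Section 5.5). Unless these are changed too, the analysis will not be one of all vaccinated patients.

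The cost is a wording amendment to these sections. The downside is small: patients given few cells may dilute the estimated effect, and the sensitivity analysis would help to show this.
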